#### **5.4. Concomitant Medication(s)**

Concomitant treatment considered necessary for the patient's well being may be given at discretion of the treating physician.

Concomitant medications and treatments, including herbal supplements, will be recorded from 28 days prior to the start of study treatment and up to 28 days post the last dose of study treatment. All concomitant medications should be recorded in the CRF including supportive care drugs (eg, antiemetic treatment and prophylaxis), and the drugs used to treat adverse events or chronic diseases, and non drug supportive interventions (eg, transfusions).

Concurrent anticancer therapy with agents other than axitinib and MK-3475 is not allowed. Medications intended solely for supportive care (ie, antiemetics, analgesics, megestrol acetate for anorexia) are allowed.

##### **5.4.1. Inhibitors and Inducers of CYP Enzymes (Axitinib)**

In vitro studies with human liver microsomes and recombinant CYP enzymes indicate that axitinib metabolism is primarily mediated by the CYP3A4/5, and to a lesser extent by CYP1A2, CYP2C19 and UGT1A1.

The concomitant use of strong CYP3A4/5 inhibitors (eg, ketoconazole, itraconazole, clarithromycin, atazanavir, indinavir, nefazodone, nelfinavir, ritonavir, saquinavir, telithromycin, and voriconazole) should be avoided. Selection of an alternate concomitant medication with no or minimal CYP3A4/5 inhibition potential is recommended. Although axitinib dose adjustment has not been studied in patients receiving strong CYP3A4/5 inhibitors, if a strong CYP3A4/5 inhibitor must be co-administered, a dose decrease of axitinib by approximately half is recommended, as this dose reduction is predicted to adjust the axitinib area under the plasma concentration vs time curve (AUC) to the range observed without inhibitors. The subsequent doses can be modified based on individual safety and tolerability. If co-administration of the strong inhibitor is discontinued, the axitinib dose should be returned (after 3 – 5 half-lives of the inhibitor) to that used prior to initiation of the strong CYP3A4/5 inhibitor.

Co-administration of axitinib with strong CYP3A4/5 inducers (eg, rifampin, dexamethasone, phenytoin, carbamazepine, rifabutin, rifapentine, phenobarbital, and St. John's wort) should be avoided. Selection of concomitant medication with no or minimal CYP3A4/5 induction potential is recommended. Moderate CYP3A4/5 inducers (eg, bosentan, efavirenz, etravirine, modafinil, and nafcillin) may also reduce the plasma exposure of axitinib and should be avoided if possible.

#### **5.4.2. Hematopoietic Growth Factors**

Primary prophylactic use of granulocyte-colony stimulating factors is not permitted during the first 6 weeks of treatment but they may be used to treat treatment emergent neutropenia as indicated by the current American Society of Clinical Oncology (ASCO) guidelines.

In subsequent cycles, the use of hematopoietic growth factors is at the discretion of the treating physician in line with local guidelines. Patients who enter the study on stable doses of erythropoietin or darbepoietin may continue this treatment, and patients may start either drug during the study at the discretion of the treating physician.

#### **5.4.3. Concomitant Surgery**

##### **5.4.3.1. Axitinib**

No formal studies of the effect of axitinib on wound healing have been conducted, however caution is advised based on the mechanism of action. If a major surgery or an interventional procedure (eg, endoscopy) is required, treatment with axitinib must be interrupted at least 24 hours before the procedure and the patient BP should be monitored closely for hypotension. Patients may resume axitinib seven days after minor surgery and 2-3 weeks after major surgery, provided that wound has completely healed and there are no wound healing complications (eg, delayed healing, wound infection or fistula).

##### **5.4.3.2. MK-3475**

Dosing interruptions are permitted in the case of medical/surgical events or logistical reasons not related to study therapy such as elective surgery, unrelated medical events, patient vacation and holidays. Patients should be placed back on study therapy within 3 weeks of the scheduled interruption, unless otherwise discussed with the sponsor. The reason for the interruption should be documented.

#### **5.4.4. Concomitant Radiotherapy**

Palliative radiotherapy to specific sites of disease is permitted if considered medically necessary by the treating physician. All attempts should be made to rule out disease progression in the event of increased localized pain. If palliative radiotherapy is needed to control bone pain the sites of bone disease should be present at baseline, otherwise, it will be considered disease progression.

#### **5.4.5. Concomitant Medications/Vaccinations (allowed & prohibited)**

Medications or vaccinations specifically prohibited in the exclusion criteria are not allowed during the ongoing trial. If there is a clinical indication for one of these or other medications or vaccinations specifically prohibited during the trial, discontinuation from trial therapy or vaccination may be required. The investigator should discuss any questions regarding this with the Sponsor Clinical Director. The final decision on any supportive therapy or vaccination rests with the investigator and/or the patient's primary physician. However, the decision to continue the patient on trial therapy or vaccination schedule requires the mutual agreement of the Investigator, the Sponsor, and the patient.

#### **5.4.6. Prohibited Concomitant Medications**

Patients are prohibited from receiving the following therapies during the Screening and Treatment Phase (including retreatment for post-complete response relapse) of this trial:

- Anti-cancer systemic chemotherapy or biological therapy.
- Immunotherapy not specified in this protocol.
- Chemotherapy not specified in this protocol.
- Investigational agents other than axitinib and MK-3475.
- Radiation therapy.

Live vaccines within 30 days prior to the first dose of trial treatment and while participating in the trial. Examples of live vaccines include, but are not limited to, the following: measles, mumps, rubella, chicken pox, yellow fever, rabies, BCG, and typhoid (oral) vaccine. Seasonal influenza vaccines for injection are generally killed virus vaccines and are allowed. However, intranasal influenza vaccines (eg, Flu - Mist®) are live attenuated vaccines, and are not allowed.

Glucocorticoids for any purpose other than to modulate symptoms from an event of clinical interest of suspected immunologic etiology. The use of therapeutic doses of corticosteroids may be approved for symptomatic treatment after consultation with the Sponsor.

There are no prohibited therapies during the Post-Treatment Follow-up Phase.

#### **5.5. Rescue Medications & Supportive Care**

##### **5.5.1. Supportive Care Guidelines**

Patients should receive appropriate supportive care measures as deemed necessary by the treating investigator including but not limited to the items outlined below:

- Diarrhea: All patients who experience diarrhea should be advised to drink liberal quantities of clear fluids. If sufficient oral fluid intake is not feasible, fluid and electrolytes should be substituted via IV infusion.

- Nausea/vomiting: Nausea and vomiting should be treated aggressively, and consideration should be given in subsequent cycles to the administration of prophylactic antiemetic therapy according to standard institutional practice. Patients should be strongly encouraged to maintain liberal oral fluid intake.
- Anti-infectives: Patients with a documented infectious complication should receive oral or IV antibiotics or other anti-infective agents as considered appropriate by the treating investigator for a given infectious condition, according to standard institutional practice.
- Anti-inflammatory or narcotic analgesics may be offered as needed. Acetaminophen/paracetamol to a MAXIMUM total daily dose of 2 g is permitted. Daily intake over 2 g is prohibited.
- Patients who need to be on anticoagulant therapy during treatment should be treated with low molecular weight heparin. If low dose heparin cannot be administered, the administration of coumadin or other coumarin derivatives or other anti-coagulants may be allowed; however appropriate monitoring of prothrombin time/International normalized ratio (PT/INR) should be performed.

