### **3.1.2. DLT Definition**

Severity of adverse events will be graded according to NCI CTCAE version 4.03 (see [Appendix 3](#)). For the purpose of Dose Finding, any of the following adverse events occurring during the DLT observation period (6 weeks) that are attributable to one or both study drugs will be classified as DLTs:

- Hematologic:

Grade 4 neutropenia;

Febrile neutropenia, defined as absolute neutrophil count (ANC)  $<1000/\text{mm}^3$  with a single temperature of  $>38.3$  degrees C (101 degrees F) or a sustained temperature of  $\geq 38$  degrees C (100.4 degrees F) for more than one hour;

Grade  $\geq 3$  neutropenic infection;

Grade  $\geq 3$  thrombocytopenia with bleeding;

Grade 4 thrombocytopenia.

- Non-hematologic:

Grade  $\geq 3$  non-laboratory toxicities despite maximum supportive therapy.

Grade  $\geq 3$  hypertension despite maximal medical therapy.

- Non-hematologic Grade  $\geq 3$  laboratory value if:

Medical intervention is required to treat the patient, or

The abnormality leads to hospitalization.

- Inability to complete at least 75% of axitinib dosing or two infusions of MK-3475 within the 6-weeks DLT observation period due to treatment-related toxicity.

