#### **4.2. Exclusion Criteria**

Patients presenting with any of the following will not be included in the study:

1. Prior systemic therapy directed at advanced RCC.
2. Prior adjuvant or neoadjuvant therapy if disease progression or relapse has occurred during or within 12 months after the last dose of treatment.
3. Prior therapy with axitinib (AG-013736).
4. Prior therapy with an anti-PD-1, anti-PD-L1, anti-PD-L2, anti-CD137, or anti-Cytotoxic T-lymphocyte-associated antigen-4 (CTLA-4) antibody (including ipilimumab or any other antibody or drug specifically targeting T-cell co-stimulation or checkpoint pathways).
5. Diagnosis of immunodeficiency or is receiving systemic steroid therapy or any other form of immunosuppressive therapy within 7 days prior to study entry.
6. Active autoimmune disease or a documented history of autoimmune disease or syndrome that requires systemic steroids or immunosuppressive agents. Patients with vitiligo or resolved childhood asthma/atopy would be an exception. Patients that require intermittent use of bronchodilators or local steroid injections and patients with hypothyroidism stable with hormone replacement will not be excluded from study.
7. Major surgery <4 weeks or radiation therapy <2 weeks of study entry. Prior palliative radiotherapy ( $\leq 10$  fractions) to metastatic lesion(s) is permitted, provided it has been completed at least 48 hours prior to the initiation of study medication and there is at least one measurable lesion that has not been irradiated.
8. Gastrointestinal abnormalities including:
  - Inability to take oral medication;
  - Requirement for intravenous alimentation;
  - Prior surgical procedures affecting absorption including total gastric resection;
  - Treatment for active peptic ulcer disease in the past 6 months;
  - Active gastrointestinal bleeding as evidenced by hematemesis, hematochezia or melena in the past 3 months without evidence of resolution documented by endoscopy or colonoscopy;
  - Malabsorption syndromes.

9. Requirement of anticoagulant therapy with oral vitamin K antagonists. Low-dose anticoagulants for maintenance of patency of central venous access device or prevention of deep venous thrombosis is allowed. Therapeutic use of low molecular weight heparin is allowed.
10. Evidence of inadequate wound healing.
11. Active bleeding disorder or other history of significant bleeding episodes within 30 days before study entry.

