**Table 5. Axitinib Dose Modifications for Drug-Related Toxicity**

Toxicity	NCI CTCAE Severity Grade	Axitinib
		Dose Modification
Hematologic Laboratory Abnormalities	Grade 1, 2 or 3	Continue at the same dose level.
	Grade 4	Withhold until recovery to Grade $\leq$ 2. Then, reduce by 1 dose level and resume treatment. Grade 4 lymphopenia not associated with clinical events, eg, opportunistic infection: study treatment may continue without interruption.
AST, ALT with total bilirubin $<2\times$ ULN and PT/INR $<1.5\times$ ULN	Grade 1	Continue at the same dose level
	Grade 2	Withhold until resolution to $<2\times$ ULN or baseline. Restart at same dose level or one lower dose level.
	Grade 3 and 4	Withhold until resolution to $<2\times$ ULN or baseline. Restart at one lower dose level.
AST/ALT Elevation with clinically significant hepatic dysfunction (ie, total bilirubin $\geq 2\times$ ULN excluding biliary obstruction or PT/INR $\geq 1.5\times$ ULN)		Permanently discontinue and follow-up per protocol.
Non-hematologic Toxicities, Laboratory Abnormalities and/or Other Drug Related Toxicities b	Grade 1	Continue at the same dose level.
	Grade 2	Continue at the same dose level.
	Grade 3	Reduce by 1 dose level.  Grade 3 toxicities controlled with symptomatic medications, or Grade 3 asymptomatic biochemistry (other than LFTs) laboratory abnormalities may continue at the same dose level per Investigator judgment.
	Grade 4	Other non-hematologic/laboratory and non-laboratory abnormalities, hold treatment until recovery to Grade $<2$ then, reduce by 1 dose level and resume treatment.  Grade 4 asymptomatic biochemistry laboratory (other than LFTs) abnormality: study treatment may continue without interruption per Investigator's judgment.
Proteinuria	Dipstick negative or shows 1+ (Grade 1)	Continue at the same dose level.
	If dipstick shows <math>>1+</math>, perform 24 hour urine collection. Dosing may continue while waiting for test results	
	<2 g proteinuria/24 hour	Continue at the same dose level.

Toxicity	NCI CTCAE Severity Grade	Axitinib
		Dose Modification
	≥2 g proteinuria/24 hours	Withhold until proteinuria is <2 g/24 hours. Repeat 24-hour urine collection for proteinuria and creatinine clearance (interval at Investigator discretion) until proteinuria is <2 g/24 hours. Then, resume at the same dose level or reduce by 1 dose level as per Investigator judgment.

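### Coumarin anticoagulants are ruled out by exclusion 9 and Protocol 5.4.5 but conditionally allowed by 5.5.1, and the PT/INR criterion in Table 5 does not address them

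*Protocol*

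**What the plan says.** Five places in the protocol bear on this.

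- **4.2, exclusion 9** makes this an entry bar: "Requirement of anticoagulant therapy with oral vitamin K antagonists". It then makes exceptions for low-dose anticoagulants used to keep a central line open or to prevent deep vein thrombosis, and adds: "Therapeutic use of low molecular weight heparin is allowed".
- **5.4.5** carries the entry bars forward: "Medications or vaccinations specifically prohibited in the exclusion criteria are not allowed during the ongoing trial". It qualifies this. A clinical indication for such a drug may (not must) mean stopping trial therapy, questions go to the sponsor, and continuing on trial therapy needs the agreement of investigator, sponsor and patient.
- **5.4.6**, the dedicated list of what "Patients are prohibited from receiving the following therapies during the Screening and Treatment Phase" introduces, names no anticoagulant.
- **5.5.1** prefers low molecular weight heparin for patients who need anticoagulation during treatment. If heparin cannot be given, "the administration of coumadin or other coumarin derivatives or other anti-coagulants may be allowed", provided PT/INR is monitored.
- **Table 5** (5.2.7) handles AST/ALT in two blocks. With bilirubin below 2 times ULN and PT/INR below 1.5 times ULN, the action depends on grade, and Grade 1 continues unchanged. The next row, "AST/ALT Elevation with clinically significant hepatic dysfunction", is defined by bilirubin at or above 2 times ULN (biliary obstruction excepted) or PT/INR at or above 1.5 times ULN. It has no grade entry, and its action is permanent discontinuation of axitinib.

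**The concern.** Sections 5.4.5 and 5.5.1 set different conditions for the same act, and neither refers to the other. Under 5.4.5, continued trial therapy alongside a drug barred at entry needs three parties to agree. Under 5.5.1, it is enough that heparin cannot be given and PT/INR is watched. Two sites could handle the same patient differently, each citing the protocol, and the deviation listing would depend on which section was read.

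Table 5 then gives the ambiguity a consequence. PT/INR serves there as a marker of liver dysfunction, but an anticoagulant that 5.5.1 permits also raises it. The bilirubin limb of the row sets aside one non-hepatocellular cause; the PT/INR limb sets aside none. At stake is the loss of axitinib, which the table makes permanent, in a patient who may be benefiting. There is also a reporting question: hepatic discontinuations whose PT/INR component has another explanation would be counted with the rest, in a combination whose liver tests Protocol 3.1 singles out for close monitoring.

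**Working it through.** The plan states no figure on this point, so the check is mainly textual, with one threshold calculation.

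**Step 1: does the on-study conflict exist?** Exclusion 9 prohibits a requirement for oral vitamin K antagonists, and coumarins are drugs of that class. Section 5.4.5 makes medications prohibited by the exclusion criteria not allowed on study. Section 5.5.1 allows coumarins on study under a condition that 5.4.5 does not mention. The conflict is therefore present, between one on-study bar (5.4.5, by reference and qualified) and one on-study permission (5.5.1).

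**Step 2: when does the discontinuation row of Table 5 apply?** It needs AST/ALT elevation and at least one of bilirubin at or above 2 times ULN or PT/INR at or above 1.5 times ULN. The table covers drug-related toxicity. An AST/ALT rise can be judged drug-related while the INR is raised by the anticoagulant; both conditions are then met as written.

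**Step 3: what INR is that?** Trigger = 1.5 × ULN. The documents give no ULN for INR and no target INR, so both are assumptions.

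- ULN 1.0: 1.5 × 1.0 = 1.50
- ULN 1.3: 1.5 × 1.3 = 1.95

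For an assumed anticoagulated INR of 2.0 to 3.0, the ratio to ULN runs from 2.0/1.3 = 1.54 to 3.0/1.0 = 3.00. All of that range is at or above 1.5. An INR below 1.50 to 1.95, with bilirubin below 2 times ULN, stays in the graded rows, where a Grade 1 rise continues at the same dose.

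**Step 4: can it reach the primary endpoint?** Protocol 3.1.2 counts as a DLT: "Inability to complete at least 75% of axitinib dosing or two infusions of MK-3475 within the 6-weeks DLT observation period due to treatment-related toxicity". The window is 42 days, and 0.75 × 42 = 31.5, so with full dosing beforehand axitinib would have to stop before about day 32. The stop must also be attributed to treatment-related toxicity; if it is not, 3.1.1.2 replaces the patient. With 10 evaluable patients one extra DLT moves the rate by 0.10. Only the step from 3/10 = 0.30 to 4/10 = 0.40 crosses the 0.33 limit; 0 to 1, 1 to 2 and 2 to 3 do not.

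**The case against.** The strongest reply is that the protocol already offers a way through. Section 5.4.5 is not absolute, and it says: "The final decision on any supportive therapy or vaccination rests with the investigator and/or the patient's primary physician". Section 5.5.1 can be read as a narrow fallback for a need that arises on treatment, after heparin. Exclusion 9 is an entry criterion, its low-dose exception names no drug class, and 5.4.6 lists no anticoagulant. It follows that a reader who infers that coumarins are barred on study in two separate places goes too far: 5.4.5 is the only on-study bar. What survives is that the route in 5.4.5 requires three-party agreement to continue trial therapy, while 5.5.1 neither requires nor mentions it.

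On Table 5, a reader might infer that anyone on a coumarin with any AST/ALT rise must stop axitinib. The text does not say so: PT/INR or bilirubin must also reach its threshold, the toxicity must be drug-related, the row is headed as clinically significant dysfunction, and 5.2.7 presents these as recommended modifications. That limits the reach of the row but does not supply the missing statement about an anticoagulant.

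A reader might also infer that the MTD estimate is at risk. That would need, within six weeks, a new need for anticoagulation in patients who entered with INR or PT below 1.5 times ULN and no thrombosis or embolism in the previous 6 months, heparin not usable, a coumarin started, the INR threshold reached, a concurrent AST/ALT rise attributed to study drug, and an early enough stop. The documents give no probability for this chain. Amendment 2 was written after primary-endpoint data collection, so new text cannot alter DLT counts. This part of the objection stands.

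**Conclusion.** The inconsistency holds and should be corrected. Exclusion 9 and 5.4.5 on one side and 5.5.1 on the other leave the status of an on-study coumarin undetermined, and Table 5 uses PT/INR as a discontinuation criterion without saying what applies when a permitted anticoagulant has raised it.

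How often the row would be reached cannot be derived from the documents. Under the assumptions of INR 2.0 to 3.0 and ULN 1.0 to 1.3, the PT/INR condition would be met throughout; with a lower INR it would not. The consequence depends on the INR reached, not on coumarin use alone. The effect on the DLT rate is secondary and remote.

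The matter remains live for patients still on treatment. Appendix 6 sets aside the original schedule and Sections 6.2, 7.2 and 7.3, but leaves 5.4.5, 5.5.1 and Table 5 in force, and its laboratory footnote still refers dose adjustment to 5.2.7.

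**What to change.** 1. Reconcile exclusion 9, 5.4.5 and 5.5.1 so that a single rule governs coumarin anticoagulants on study, with cross-references between the sections.
2. Reconcile the PT/INR criterion in Table 5 with whatever 5.5.1 then permits. Which clinical rule applies is for the sponsor to decide.
3. In the DLT listing (SAP 8.3.3.1) and the listings of withdrawals from treatment due to adverse events (SAP 8.3.3.2), add a flag for events triggered by PT/INR in patients on an anticoagulant at the time.

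The cost is clarifying text in four protocol places and one derived flag. Concomitant medications are already recorded on the CRF (Protocol 5.4), and PT and INR are required tests in Table 8. One limit should be noted: under Appendix 6, coagulation testing follows local standard of care, so the flag may be incomplete for late cycles unless the PT/INR value behind a discontinuation is recorded with the event.

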#### **5.5.2. Management of MK-3475 Infusion Reactions**

Signs and symptoms usually develop during or shortly after drug infusion and generally resolve completely within 24 hours of completion of infusion.

**Table 7** below shows treatment guidelines for patients who experience an infusion reaction associated with administration of MK-3475.

**Table 7. MK-3475 Infusion Reaction Treatment Guidelines**

NCI CTCAE Grade	Treatment	Premedication at subsequent dosing
Grade 1 Mild reaction; infusion interruption not indicated; intervention not indicated	Increase monitoring of vital signs as medically indicated until the patient is deemed medically stable in the opinion of the investigator	None
Grade 2 Requires infusion interruption but responds promptly to symptomatic treatment (eg, antihistamines, NSAID, narcotics, IV fluids); prophylactic medications indicated for < = 24 hours	
Stop Infusion and monitor symptoms.  Additional appropriate medical therapy may include but is not limited to:
 
IV fluid  Antihistamines  NSAIDS  Acetaminophen  Narcotics
 
Increase monitoring of vital signs as medically indicated until the patients is deemed medically stable in the opinion of the investigator.  If symptoms resolve within one hour of stopping drug infusion, the infusion may be restarted at 50% of the infusion rate (eg, from 100 mL/hr to 50 mL/hr). Otherwise dosing will be held until symptoms resolve and the patient should be premedicated for the next scheduled dose.
 
Patients who develop Grade 2 toxicity despite adequate premedication should be permanently discontinued from further trial treatment administration.
	Patients may be premedicated 1.5 hour ( $\pm$ 30 minutes) prior to infusion of MK-3475 with:  Diphenhydramine 50 mg PO (or equivalent dose of antihistamine).  Acetaminophen 500-1000 mg PO (or equivalent dose of antipyretic).
Grades 3 or 4 Grade 3; Prolonged (ie, not rapidly responsive to symptomatic medication and/or brief interruption of infusion); recurrence of symptoms following initial improvement; hospitalization indicated for other clinical sequelae (eg, renal impairment, pulmonary infiltrates)  Grade 4: Life-threatening; pressor or ventilatory support indicated	
Stop infusion.  Additional appropriate medical therapy may include but is not limited to:
 
IV fluids  Antihistamines  NSAIDS  Acetaminophen  Narcotics  Oxygen  Pressors  Corticosteroids  Epinephrine**
 
Increase monitoring of vital signs as medically indicated until the patient is deemed medically stable in the opinion of the investigator.  Hospitalization may be indicated.  **In cases of anaphylaxis, epinephrine should be used immediately.
 
Patient is permanently discontinued from further trial treatment administration.
	No subsequent dosing
Appropriate resuscitation equipment should be available in the room and a physician readily available during the period of drug administration.		

